The study will be performed at the Baylor College of Medicine. Approval from Site Review Authority will be obtained. Subjects will be recruited from outpatient clinics at Baylor College of Medicine.

We propose a randomized crossover trial (Phase I/II) to evaluate acceptability as well as short (1 week) and intermediate (6 week) benefits and effectiveness of Orthofeet in reducing foot pain, increasing daily physical activities, and improving functional performance in ambulatory patients suffering from foot pain.

We are proposing a clinical study at the Baylor College of Medicine, to evaluate short and intermediate benefits and effectiveness of a novel pain relief footwear, called Orthofeet. This is a randomized crossed over trial. The duration of the study would be 12-week. We will recruit 50 eligible ambulatory adults (age 50 years or older) with moderate to severe self-reported foot pain. Participants will be randomly assigned to Group A (25 subjects) and Group B (25 subjects). There is no difference in assessments or eligibility between Group A and Group B, the only difference is when they have the opportunity to try the shoes for 6 weeks. Group A will receive a pair of Orthofeet shoes with adjustable insoles and will be asked to wear it every day activities of daily living for duration of six weeks. Participants will be also encouraged to wear the shoes inside of home if possible. Group B will be followed for duration of six weeks. At six weeks the groups will be switched and group B will receive a pair of Orthofeet shoes with adjustable insoles and Group B will follow-up for six weeks without Orthofeet shoes. Participants will be assessed at baseline, week-1, week-6, week 7, and week 12.

The primary outcome includes changes compared to baseline in foot pain intensity.

The secondary outcomes includes changes compared to baseline in various metrics of daily physical activities (e.g., daily step, longest walking bout, cadence, standing duration, and standing duration).

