Patient acceptability: We will use a Technology Acceptance Model (TAM) survey adapted for footwear to determine perceived benefit, perceived ease of use, acceptability, and attitude toward daily use. Patient acceptability will be assessed at the end of week 6 active use of OrthoFet (6- week for Group A and 12 week for group B) or the conclusion of the study for early endpoint.

Ancillary Measurements Patient-reported outcomes: Self-reported pain level will be extracted from FACT-G; ADL will be assessed using Katz Index of Independence in ADL; Community engagement will be assessed using the Life-Space Assessment questionnaire; The Fall Efficacy Scale-International (FES-I) questionnaire to determine concern for falls. Anxiety will be assessed using the Beck Anxiety Inventory questionnaire; cognition will be assessed using Montreal Cognitive Assessment (MoCA). Patient-reported outcomes will be assessed at baseline, week 6 and week 12. The subjects will not be advised or counseled based on the results of the questionnaires, these tools are not diagnostic, but the coordinators will try to provide possible resources if asked by the subject.

Digital Photographs , may take digital photographs of the subjects while performing exercise or during assessments for the purpose of publication (conferences/manuscripts). **Physical frailty:** Frailty will be assessed by trauma-specific frailty index and a validated wearable frailty meter technology.

Health related questionnaires: A series of health related questionnaires will be used to evaluate your quality of life , fear of falling, fall history, mobility, activities of daily living, depression, frailty, mental exams, foot examinations, pain intensity levels. Your medical history (from your clinic chart such as: medication use, prior surgery, diagnosis, progress notes, etc.) and demographic information will be obtained, such as age, gender, weight, and height. These questionnaires are asked to review the subject holistically and assess changes in their overall health, including mental and physical, over the 3 month span. The relevance to foot pain is to see how these components of health are related to foot pain such as finding a connection between their foot pain and fear of falling doing different activities.

At Visit 2 (1 Week Follow Up) the participant is called by the research staff to complete the pain questionnaire, document adverse events, and answer any study-related questions.

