At Visit 3 (6 Week Follow Up) the participant will complete all the same assessments and questionnaires as baseline. At this visit, Group A will stop wearing OrthoFet shoes and continue the study without them. Group B will be supplied with OrthoFet shoes to wear for the rest of their study participation until 12 Week Follow Up.

At Visit 4 (7 Week Follow Up) the participant is called by the research staff to complete the pain questionnaire, document adverse events, and answer any study-related questions.

At Visit 5 (12 Week Follow Up) the participant will complete all the same assessments and questionnaires as baseline. All participants will return OrthoFeet shoes by this point.

Section G: Sample Size/Data Analysis

G1. Sample Size

How many subjects (or specimens, or charts) will be used in this study?

Local: 50 Worldwide: 50

Please indicate why you chose the sample size proposed:

This is a proof of concept study. The sample size is 50 eligible participating in a randomized crossover study. The sample size is convenient and is selected to detect a between group difference for the primary outcome (change in foot pain) with medium effect size (Cohen's $d=0.50$) with a dropout rate of 15%, alpha of 5%, and power of 80%. The anticipated effect size was estimated from our prior study (Najafi et al, Journal of Foot and Ankle Research, 2014) in which we observed a significant drop in foot pain after orthotic therapy compared to sham orthotics. Based on this pilot study, we will propose a Phase II study to validate the observed effect in the follow-up study.

G2. Data Analysis

Provide a description of your plan for data analysis. State the types of comparisons you plan (e.g. comparison of means, comparison of proportions, regressions, analysis of variance). Which is the PRIMARY comparison/analysis? How will the analyses proposed relate to the primary purposes of your study?

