We will utilize REDCap, a HIPAA compliant database application, to ensure uniformity of data entry. A qualified postdoc will provide ongoing oversight and reporting of data quality, including missing data, timeliness of data entry, responsiveness to data queries, etc. Data meetings will be held twice monthly, and specific challenges will be addressed. Baseline descriptive statistics among randomized groups will include demographic and clinical variables, summarized as mean (SD) (or median, IQR) for continuous variables and frequency (percent) for categorical variables. For each baseline variable, the magnitude of group differences will be summarized as pairwise standardized mean/proportion differences (group difference divided by SD). Distributions of continuous trial outcomes will be evaluated for normality; normalizing transformations will be completed if needed. Group comparisons on primary outcomes will be by intent to treat. Statistical testing on the outcomes will be evaluated at alpha=0.05 each. Group comparisons on secondary and exploratory outcomes will control for multiple comparisons (false discovery rate) using the Benjamini-Hochberg method. In all models, outcomes will be summarized as mean group levels (with 95% CI) and mean group differences (with 95% CI). Results of the user experience questionnaires will be calculated as median (range) for each Likert-scale question. Unpaired t-tests, Mann-Whitney u-tests, and Chi-square will be used for baseline between groups comparison to verify effectiveness of randomization. To evaluate the effect of gender as biological variable, we will examine whether acceptability and benefits of footwear (between groups as well as compared to baseline) are different between men and women.

Section H: Potential Risks/Discomforts

H1. Potential Risks/Discomforts

Describe and assess any potential risks/discomforts; (physical, psychological, social, legal, or other) and assess the likelihood and seriousness of such risks:

The risk to participants of this study is considered to be minimal in a controlled environment with an attendant present. This research routine will not place subjects at higher risk than normal activities of daily living, and no more risk of harm or discomfort is associated with these tests than the discomfort normally incurred while performing normal activities.

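### The primary test of foot pain is not fixed: two time horizons and two possible contrasts are left open, and the choice decides both the false-positive rate and the power

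*Combined protocol and SAP*

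**What the plan says.** **Outcome.** Section F1 states: "The primary outcome includes changes compared to baseline in foot pain intensity". Section F2 measures foot pain with the Foot Function Index (FFI), which yields a total and three sub-scale scores, at baseline and weeks 1, 6, 7 and 12.

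**Horizons.** F1 describes the trial as one "to evaluate acceptability as well as short (1 week) and intermediate (6 week) benefits and effectiveness of Orthofeet in reducing foot pain". Neither horizon is ranked first.

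**Design.** F1: "At six weeks the groups will be switched and group B will receive a pair of Orthofeet shoes". F2, Visit 3: "At this visit, Group A will stop wearing OrthoFet shoes and continue the study without them".

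**Sample size.** G1 calls the number 50 convenient and also "selected to detect a between group difference for the primary outcome (change in foot pain"), with Cohen's d = 0.50, 15% dropout, 5% alpha and 80% power.

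**Analysis.** The G2 form asks: "Which is the PRIMARY comparison/analysis". The answer says that primary outcomes, in the plural, are compared between groups by intent to treat, and then: "Statistical testing on the outcomes will be evaluated at alpha=0.05 each". Benjamini-Hochberg control is applied to secondary and exploratory outcomes. G2 names no primary visit, FFI score, model, period term or sequence term.

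**The concern.** One primary outcome is not yet one primary test. Two choices are open:

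- **Horizon:** one week or six weeks in the shoes.
- **Contrast:** the difference between groups in period 1 only, or the within-participant difference between time in and out of the shoes, using both periods.

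The FFI score is a smaller matter. F1 speaks of pain intensity, which points to the pain sub-scale, so this needs only a clarifying word.

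Two things are at stake. First, the multiplicity control in G2 does not reach the primary outcome. Several foot-pain tests could each be run at 0.05, or one could be chosen after the data are seen, while G1 plans on 5%. Second, the two contrasts have very different power, so a reader cannot tell what the trial is sized to detect. Strict error control matters less in a pilot than in a confirmatory trial. But G1 says that a Phase II study will follow to validate the observed effect, and a result selected among visits or contrasts is a poor basis for that study.

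**Working it through.** **Inputs from the documents.** N = 50 (25 per group), 15% dropout, d = 0.50, alpha 5%, power 80%. Completers: 50 × 0.85 = 42.5, taken as 42 (21 per arm).

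**Assumptions.** Two-sided tests. Pain scores at all visits have equal variance σ² and a common within-participant correlation r. No carryover in the power figures.

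**1. Does the stated sample size reveal the contrast?**

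- Period-1 group comparison: n per arm = 2(1.960 + 0.842)²/0.50² = 62.8, so 63. Total 126 completers; 126/0.85 gives 149 enrolled.
- Crossover contrast, d on the SD of the within-participant difference: (1.960 + 0.842)²/0.50² = 31.4, so 32 (34 with the t distribution). 34/0.85 gives 40 enrolled.
- Crossover contrast, d on the SD of a single score: 51 enrolled at correlation 0.35 and 48 at 0.40. The documents give no correlation.

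The stated inputs alone do not give 50 under either contrast, so G1 does not show which was meant.

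**2. Power at d = 0.50, 42 completers, alpha 0.05**

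- Period 1, 21 per arm: noncentrality 0.50 × √(21/2) = 1.62, power about 35%.
- Crossover: noncentrality 0.50 × √42 = 3.24, power about 89%.

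Under the assumed structure the two figures compare like with like. A change from baseline and a week-6 minus week-12 difference both have SD σ√(2(1 − r)), so d = 0.50 on either is the same raw effect. If d is instead on the SD of a single score, crossover power runs from 61% (r = 0) through 76% (r = 0.3) and 89% (r = 0.5) to 98% (r = 0.7).

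**3. Correlation between the candidate tests.** Write Y0, Y1, Y6, Y12 for pain at those weeks.

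- One-week and six-week change in period 1: Cov(Y1 − Y0, Y6 − Y0) = r − r − r + 1 = 1 − r; each variance is 2(1 − r); correlation 0.5.
- Six-week change and crossover: Cov(Y6 − Y0, Y6 − Y12) = 1 − r − r + r = 1 − r; correlation again 0.5.

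**4. Chance of at least one false positive, each test at 0.05, either counting**

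| Tests counted | Result |
|---|---|
| One test fixed in advance | 4.8% to 5.1% (simulated) |
| Week 1 or week 6, period 1 | 9.1% (simulated 8.8% to 9.3%) |
| Period 1 or crossover, six weeks | 9.1% (simulated 8.9% to 9.5%) |
| Two horizons × two contrasts | 16.6% to 17.1% (simulated) |

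The simulations used 42 completers, 20,000 null trials per setting and correlations from 0.3 to 0.8. Should two tests be more closely correlated than 0.5, the rate falls: 8.3% at 0.7, 7.0% at 0.9, 6.5% at 0.95 and 5.7% at 0.99. Zero correlation (9.75%) is not plausible for two changes that share one baseline.

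**The case against.** The strongest reply is that F1 names a single primary outcome, and that G1 and G2 consistently speak of differences between groups, which leans towards a plain group comparison. No passage describes an on-shoes versus off-shoes contrast; that candidate is inferred from the crossover design. The 0.05 in G2 is set for each outcome, not for each visit or contrast, and one test fixed in advance keeps 5%. This is also a convenience-sized proof-of-concept study.

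Much of this stands. A reader might infer that the plan runs several unadjusted primary tests and so has an error rate of 9% or more. The documents do not support that: they neither state nor exclude that success on any one test counts. Nor do they support multiplying by all four FFI scores, which would give 16 tests and a simulated 31% to 43%, because F1's wording largely settles the score.

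The reply does not close the gap. Between-group wording does not rank the two horizons. If it does mean period 1, that test has about 35% power against the 80% claimed, and the second half of the crossover has no stated primary role. That reading would also have to be written down.

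**Conclusion.** The concern holds in this form: the primary test of foot pain is under-specified in its visit and its contrast, and G2's multiplicity control does not cover the primary outcome. If either of two such tests counts, the false-positive chance is about 9%, and about 17% if any of four counts, against the 5% in G1. These rates are conditional on an either-counts rule that the plan does not state, and on equal variances and correlations.

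The power consequence needs no such rule and is the larger one: about 89% or about 35% at d = 0.50 with 42 completers, depending on the contrast, with the 89% resting on d being the standardised within-participant difference. A reader might infer that the trial is simply underpowered. That follows only if period 1 is the primary comparison, which the documents do not say.

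This should be corrected before analysis. It does not invalidate the design.

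**What to change.** **F1 and G2:** name one primary test at two-sided 0.05. One workable choice, which the documents do not force, is the FFI pain sub-scale at the end of each six-week period (weeks 6 and 12), on-shoes versus off-shoes. Estimate it from a mixed model with treatment, period and sequence, a participant random effect and the pre-randomisation score as covariate, including all randomised participants with data. Weeks 6 and 12 suit this because they repeat the full baseline assessments, whereas weeks 1 and 7 are telephone contacts (F2, Visit 2: "At Visit 2 (1 Week Follow Up) the participant is called by the research staff to complete the pain questionnaire"). Both periods share one baseline, so for completers the on-minus-off difference is the same in scores or in changes, in keeping with F1's definition.

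**G1:** say which contrast d = 0.50 and 80% power refer to.

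**Sensitivity analysis:** no washout is described, so report the baseline-adjusted week-6 group difference from period 1 with its 95% CI. At about 35% power it can check the estimate but cannot rule out carryover.

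**Other pain tests:** put the one-week contrast (weeks 1 and 7), the FFI total and the other sub-scales in the existing Benjamini-Hochberg family. Note that at week 7 Group A has been out of the shoes for only one week. If both horizons are to stay primary, say so and use Holm.

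**Cost:** a few sentences and no new data. The one-week result loses primary status. Under Holm, first-step power (alpha 0.025) falls from about 89% to 82% for the crossover contrast, or from about 35% to 25% for period 1.

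### Adjustment for baseline FFI is not prespecified for the between-group comparison of foot pain; the plan instead tests baseline differences, which cannot verify randomisation.

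*Combined protocol and SAP*

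**What the plan says.** Section F1 (Design) defines the outcome: "The primary outcome includes changes compared to baseline in foot pain intensity". Section G1 (Sample Size) says that 50 participants were chosen "to detect a between group difference for the primary outcome (change in foot pain) with medium effect size", with 15% dropout, alpha 5% and power 80%. Section F2 (Procedure) measures foot pain by the revised FFI at baseline and at weeks 1, 6, 7 and 12.

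Section G2 (Data Analysis) says of the main analysis that "Group comparisons on primary outcomes will be by intent to treat". It promises group means and mean differences with 95% confidence intervals from models, but it does not say what those models are or what covariates they contain.

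For baseline data, G2 plans two things. For each variable, "the magnitude of group differences will be summarized as pairwise standardized mean/proportion differences". It also states that "Unpaired t-tests, Mann-Whitney u-tests, and Chi-square will be used for baseline between groups comparison to verify effectiveness of randomization". No action is attached to the result of any of these tests.

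**The concern.** If allocation was properly random, every baseline difference is due to chance, so a baseline p-value tests a hypothesis already known to be true. It can mislead both ways. Across many variables some will fall below 0.05. With 25 per group, a gap in baseline pain large enough to matter can easily pass as non-significant.

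What protects the pain comparison is a covariate fixed in advance, and the plan does not fix one. A change score does not do this work. Because of regression to the mean, the group that starts higher is expected to fall further even if the shoes do nothing. At stake are precision in a small trial and an unsettled choice of primary model, which could then be made after the baseline comparison has been seen.

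**Working it through.** **Inputs.** From the documents: 25 per group (F1); d = 0.50, 15% dropout, alpha 5%, power 80% (G1). Completers: 50 × 0.85 = 42.5, taken as 21 per group. Assumed, because the documents do not give them: two-sided alpha; d on the SD of the change score; equal variances at baseline and follow-up; baseline-to-follow-up correlation r from 0.3 to 0.9.

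**The plan's own figure.** A two-sample t-test with d = 0.50, two-sided 5% and 80% power needs 63.8, so 64 per group: 128 completers, or 128/0.85 = 151 recruited. The stated 50 is not reproduced for a between-group comparison. That is a separate issue; it matters here only because the starting power is low.

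**Baseline tests.**
- False alarms: for k independent tests, P(at least one p < 0.05) = 1 − 0.95^k, which is 40% at k = 10 and 64% at k = 20. Both the count and the independence are assumptions. Many of the measures in F2 are related, so these figures are only a guide.
- False reassurance: in SD units, the SE of a baseline difference is √(2/25) = 0.283. Significance needs 2.011 × 0.283 = 0.57 SD. A chance gap of at least 0.3 SD in either direction has probability 2 × [1 − Φ(0.3/0.283)] = 29%.
- Effect of an undetected 0.3 SD gap on a change-score contrast: (1 − r) × 0.3 = 0.21, 0.15 or 0.09 raw FFI SD at r = 0.3, 0.5 or 0.7. At r = 0.5 the raw and change-score SDs coincide, so the shift is 0.15 against a target of 0.50. The shift is conditional on the gap that occurred; averaged over all randomisations it is zero. Adjustment removes it in expectation.

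**Precision of a between-group comparison.** With unit variances, the change score has variance 2(1 − r) and the baseline-adjusted score 1 − r². The ratio is (1 − r²)/[2(1 − r)] = (1 + r)/2. Power is from the two-sample t-test with 21 per group and effective d = 0.50/√[(1 + r)/2], ignoring the one degree of freedom spent on the covariate.

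| r | Variance ratio | Variance cut | Effective d | Power |
|---|---|---|---|---|
| Unadjusted change | 1 | – | 0.500 | 35.3% |
| 0.3 | 0.65 | 35% | 0.620 | 50.1% |
| 0.5 | 0.75 | 25% | 0.577 | 44.7% |
| 0.7 | 0.85 | 15% | 0.542 | 40.3% |
| 0.9 | 0.95 | 5% | 0.513 | 36.8% |

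A normal approximation gives values 1 to 2 points higher.

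**Within-person contrast.** Each participant has one baseline and two period outcomes. In the difference between periods, (period 1 − baseline) − (period 2 − baseline), baseline drops out. In a simulation (5,000 replicates, 21 per group, r = 0.3 to 0.7), adding baseline as a covariate changed the SE of this contrast by about −3% to +1%.

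**The case against.** The strongest reply is that the plan never commits to an unadjusted analysis. A reader might infer from the outcome definition that a raw change score will be compared by t-test. The documents do not support that. G2 speaks of models without describing them, and it confines the named tests to baseline comparisons. A change outcome is also compatible with adjustment: with baseline as a covariate, analysing change or follow-up score gives the same treatment estimate. This stands, so the defect is that adjustment is not prespecified.

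Second, this is a crossover, and for a complete-data within-person contrast the gain essentially vanishes. This also stands. However, G1 sizes the trial on a between-group difference in change and G2 speaks of group comparisons, so the between-group contrast is the one the text describes. The plan should say which contrast is primary.

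Third, the baseline tests trigger nothing. A reader might infer that a significant result would change the model, or that the tests bias the treatment estimate. Nothing in G2 says or implies either. The tests are redundant, and deleting them changes no result by itself.

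Fourth, the size of the gain depends on r, the SD behind d and the number of baseline variables, none of which is given. That is why ranges are shown.

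**Conclusion.** The point holds for any between-group comparison of FFI pain. Baseline FFI is collected, but neither a primary model nor a baseline covariate is prespecified, and the planned tests are no substitute. Against an unadjusted change score, adjustment cuts the variance by 35% to 5% for r from 0.3 to 0.9 and lifts power from 35% to between 50% and 37%. This assumes 21 completers per group, two-sided 5% and d = 0.50 on the change-score SD. The gain is useful if r is low or moderate and small if r is near 0.9.

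A reader might also infer that adjustment rescues the sample size. On these assumptions it does not: the best case is 50% against a stated 80%. Nor does it help a complete-data within-person contrast. The omission does not invalidate the primary comparison. It gives up precision and leaves the primary model open in a small trial meant to inform a further study.

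**What to change.** In G2:

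1. State which contrast is primary (between groups at the end of the first period, or within person across periods) and name its model.
2. For any between-group comparison of FFI pain, prespecify baseline FFI as a covariate: ANCOVA at a single time point, or baseline as a covariate in a mixed model. The outcome may stay as change or become the follow-up score; the adjusted treatment estimate is the same.
3. If the within-person contrast is primary, specify period and sequence terms, and do not claim a precision gain from the single baseline.
4. Delete the baseline significance tests and keep the standardised differences as the description of balance.

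The cost is a few sentences of plan wording. Baseline FFI is already collected, so no extra data, visits or participants are needed.

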Exclusion criteria: Patients with plantar ulcer Patients with major foot deformity (e.g., Charcot foot, Pes Cavus) Patients with lower extremity amputation including minor amputation. Foot pain because of nail disorder or keratotic lesions (e.g. corns, calluses) Patients with unstable conditions (e.g., recent stroke, anticipated changes in medication regime) Acute fractures of the foot Participation in an interventional Study such as exercise intervention within the last 30 days Non-ambulatory or unable to stand without help or walk a distance of at least 6 feet without assistance. Patients with major cognitive impairment or major depression Patients who are unable or unwilling to participate in all procedures and follow up evaluations

F2. Procedure

7) The research will be conducted at the following location(s): Baylor College of Medicine and Baylor St. Luke's Medical Center (BSLMC). Duration of study: 12 weeks

Research staff may contact you for any study related questions throughout your participation in the study

Visit 1 (Baseline): Maximum duration 120 minutes

Screening: Measurements will take place at your home, or in Baylor Clinic based on your preference. Participants will be randomly placed in either Group A or Group B. Group A wears the OrthoFet shoes from baseline to 6 week follow up and Group B wears OrthoFet shoes from 6 week follow up to 12 week follow up.

All the same assessments and questionnaires are completed at each visit for all participants.

Foot Pain: Foot pain will be assessed by the revised Foot Function Index (FFI). FFI was developed in 1991 to measure the impact of foot pathology on function in terms of pain, disability, and activity restriction. It is a self-administered index consisting of 23 items divided into 3 sub-scales. Both total and sub-scale scores are produced. The FFI has been shown to be a reasonable tool for use with low functioning individuals with foot disorders, patients with rheumatoid arthritis, and non-traumatic foot or ankle problems. It can be used in both clinical and research settings. Foot pain will be assessed at baseline, week-1, week-6, week-7, and week-12.

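### The analysis by gender counts uncontrolled change from baseline as footwear benefit; the main randomised comparisons are not affected

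*Combined protocol and SAP*

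**What the plan says.** Section G2 closes with the analysis by gender. It will examine whether acceptability and "benefits of footwear (between groups as well as compared to baseline) are different between men and women". The words "between groups as well as compared to baseline" thus name change from baseline there as a second measure of benefit beside the group comparison.

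Elsewhere the plan points to group comparisons:

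- F1 defines the outcome variable: "The primary outcome includes changes compared to baseline in foot pain intensity". The secondary outcomes are defined in the same way: "The secondary outcomes includes changes compared to baseline in various metrics of daily physical activities".
- G2 assigns the tests: "Group comparisons on primary outcomes will be by intent to treat", and "Group comparisons on secondary and exploratory outcomes will control for multiple comparisons (false discovery rate) using the Benjamini-Hochberg method".
- G1 sizes the trial on a between-group difference in change in foot pain.

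On timing, F2 says that "Group B wears OrthoFet shoes from 6 week follow up to 12 week follow up"; Group A wears them for the first six weeks. Foot pain is scored at baseline and Weeks 1, 6, 7 and 12. G2 does not say whether Group B's change on the shoes is taken from Week 0 or Week 6, and it names no crossover model.

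**The concern.** People who join a trial because of foot pain tend to score lower later whether or not they are treated. Their score at entry is on average a high one, and pain may also drift over the following weeks. A change from baseline contains both effects as well as any shoe effect. If each sex's change is presented as benefit, some or all of it may be natural course. If the changes are compared between men and women, a difference may arise because one sex entered with worse pain or has a different natural course.

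Group B adds a second problem. It receives the shoes only at Week 6, so its Week 12 change from Week 0, read alone, covers six weeks without shoes and six with them.

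At stake is a claim of benefit in one sex, or of a sex difference, that could be carried into the Phase II study that G1 says will follow. Acceptability is not touched: F2 has it assessed only at the end of shoe use, so it has no baseline.

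**Working it through.** The documents give no estimate of untreated change, so there is no figure of the plan's to reproduce. The check is algebra first, then illustrative sizes.

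**Inputs from the documents.** 50 participants, 25 per group, switch at Week 6 (F1); 15% dropout (G1). Completers: 50 × 0.85 = 42.5, taken as 42, or 21 per group.

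**Assumptions.** Test-retest correlation r; an entry cut-off c on the pain score, in population SD from the mean; drift per six weeks; normal scores; no true shoe effect in the size calculations.

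**Step 1. What each comparison estimates.** Let S be the shoe effect (a fall in pain), R regression to the mean (complete by Week 6), and D1 and D2 the drift in Weeks 0-6 and 6-12. Assume no carryover.

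| Comparison | Expected fall |
|---|---|
| Group A, Week 0 to 6 | S + R + D1 |
| Group B, Week 0 to 6 | R + D1 |
| A minus B at Week 6 | S |
| Group B, Week 0 to 12 | S + R + D1 + D2 |
| Group B, Week 6 to 12 | S + D2 |

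In the crossover contrast the baseline drops out: (Week 6 − Week 0) − (Week 12 − Week 0) = Week 6 − Week 12. The expected value of that difference in pain score is −S + D2 in Group A and S + D2 in Group B. Half of B minus A is S.

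**Step 2. Men (m) versus women (f).** The before-after reading in Group A gives (Sm − Sf) + (Rm − Rf) + (D1m − D1f). The randomised reading gives Sm − Sf. A fall shared by both sexes cancels in the first; a fall that differs between them does not.

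**Step 3. Size of R.** Expected fall = (1 − r) × φ(c) / (1 − Φ(c)). The ratio is 0.3989/0.5 = 0.798 at c = 0 and 0.3521/0.6915 = 0.509 at c = −0.5.

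| r | c = 0 | c = −0.5 | Spurious sex difference if one sex has each cut-off |
|---|---|---|---|
| 0.5 | 0.399 | 0.255 | 0.144 SD |
| 0.7 | 0.239 | 0.153 | 0.086 SD |
| 0.8 | 0.160 | 0.102 | 0.058 SD |

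For drift, 0.2 SD per six weeks in one sex and 0.1 SD in the other gives a spurious difference of 0.1 SD at Week 6. For Group B at Week 12 measured from Week 0 it is 2 × 0.1 = 0.2 SD.

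**Step 4. Error rates with no shoe effect.** Simulation of 4,000 trials per scenario, 21 completers per group, both sexes together, two-sided 5%. *Pooled on-shoe* is Group A at Week 6 and Group B at Week 12, each against Week 0.

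| r, cut-off, drift per 6 weeks | Group A before-after | Pooled on-shoe vs Week 0 | A vs B change, Week 6 | Crossover contrast |
|---|---|---|---|---|
| 0.7, none, 0 | 5.0% | 4.8% | 4.7% | 5.0% |
| 0.7, −0.5, 0 | 14% | 24% | 5.4% | 4.5% |
| 0.7, 0, 0 | 29% | 54% | 4.7% | 4.6% |
| 0.5, 0, 0 | 48% | 78% | 4.8% | 5.0% |
| 0.7, none, 0.1 | 9% | 23% | 4.6% | 4.7% |
| 0.7, none, 0.2 | 20% | 69% | 5.0% | 5.2% |
| 0.7, 0, 0.1 | 53% | 92% | 4.5% | 5.6% |

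The randomised contrasts hold close to 5% throughout. The two before-after columns are paired tests that the plan does not name. They show what would follow if change from baseline were tested, not what the plan's main analysis will do.

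**The case against.** A reader might infer from the quoted words, and from the definition of the primary outcome, that the trial as a whole will judge benefit against baseline, so that natural course would be reported as a shoe effect. The documents do not support that. The words stand in one sentence about gender. Change from baseline in F1 is the outcome variable, and G1 and G2 compare it between randomised groups, with a concurrent shoe-free group in Weeks 0-6. Step 1 shows that shared regression and drift then cancel.

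Three further objections carry weight:

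- *G2 names no within-group test.* The before-after error rates therefore cannot be quoted as the plan's error rates.
- *The question is a difference between the sexes.* A fall common to both cancels. What remains is any difference in severity or natural course, and any presentation of each sex's change as benefit.
- *The selection effect may be small.* F1 describes moderate to severe pain, the inclusion criteria ask only for self-reported foot pain, and the advertisement in Section R invites mild to severe pain. No threshold on the Foot Function Index is set. Selection on something other than the analysed score would produce less regression to the mean.

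The Week 0 problem is also limited: Week 0 cancels within the crossover contrast and misleads only where Group B's Week 12 change is read alone.

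What stands is that, followed as written, the gender analysis accepts an uncontrolled change as a measure of benefit, and nothing in G2 labels it descriptive.

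**Conclusion.** The point holds for the analysis by gender only. There, one of the two stated readings of benefit cannot isolate a shoe effect, and a sex difference in it can arise with no difference in response to the shoes. Group B's change from Week 0 to Week 12 is a poor measure of six weeks of wear whatever the entry severity.

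The size is not known from the documents. Under the assumptions shown (r 0.5 to 0.8, cut-off at the mean or 0.5 SD below it), the untreated fall is 0.10 to 0.40 SD. The spurious sex difference is 0.06 to 0.14 SD if the sexes differ by 0.5 SD in effective cut-off. These are illustrations.

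The primary and secondary group comparisons are not biased by shared regression to the mean or drift, and this point gives no reason to doubt them.

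**What to change.** In G2:

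1. Remove change from baseline as a measure of benefit in the gender sentence.
2. State that footwear benefit, overall and by sex, is judged on the randomised on-shoe versus off-shoe contrast with a period term; by sex, on the treatment-by-sex interaction with its 95% CI.
3. Present change from baseline descriptively, as means with 95% CI. Use Week 6 as Group B's pre-shoe reference. That removes the shoe-free weeks but still contains any drift in Weeks 6-12, so it stays descriptive.
4. Reconcile the three descriptions of entry pain severity (F1 design text, inclusion criteria, Section R).

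The change needs no new data, visits or participants. It has two costs. Before-after changes within a group can no longer be claimed as benefit. The interaction will also be imprecise with 50 participants: if the overall effect has variance V and the sexes are equally represented with equal variance, each sex's effect has variance 2V and their difference 4V, so the standard error is twice that of the overall effect. It is larger still if the sexes are unequal in number. The result by sex should therefore be described as exploratory.
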